Clinical evaluation of DAILIES TOTAL 1® Multifocal compared to
1-Day Acuvue® Moist® Multifocal in a Japanese population.

CLINICAL STUDY PROTOCOL

Alcon Japan Ltd.

[name]

Protocol No.: CLJ369-P001 / NCT03341923

Project No.: A03218

Version 1.1: 22 JAN, 2018

SUMMARY

Protocol No.	CLJ369-P001
Objective	The purpose of this clinical study is to demonstrate non-inferiority of DAILIES TOTAL1® (DT1MF) Multifocal contact lenses to 1-DAY ACUVUE® Moist® Multifocal (AMMF) for Investigator-graded successful lens centration in Japanese population.
Subjects	Habitual presbyopic soft/ silicone hydrogel contact lens wearers (multifocal (MF) lenses only) with a near spectacle ADD of +0.50D to +2.50D (inclusive).
Study Design	Prospective, Multi-Center, Single Masked (Subject), Randomized, Crossover study.
Investigational Products	DAILIES TOTAL1® Multifocal (DT1MF) 1-DAY ACUVUE® Moist® (Multifocal) (AMMF)
Variables	
[Efficacy]
 
Primary Efficacy:
 
Investigator-graded successful lens centration of “Optimal” after 14±3 days of wearing.
 

 

	 
[Safety]
 
 • Biomicroscopy findings: Slit-lamp examination • Best corrected visual acuity with trial frame • Adverse events • Device deficiencies
Usage	Follow the direction for use.
Examinations Schedule	
 • Visit 1: Study start day (Baseline visit) • Visit 2: Follow up visit after 14±3 days of Visit 1 • Visit 3: Follow up visit after 14±3 days of Visit 2
No. of Subjects	
Required: 120 subjects (at least 50% should be wearing Proclear 1 day MF contact lenses habitually, 1 eye per 1 subject is the analysis target)
 
Planned: 134 subjects

Study period	From NOVEMBER 2017 to OCTOBER 2018
Study Sponsor	Alcon Japan Ltd.
GCP	
This study will be conducted in accordance with Good Clinical Practice (GCP) and the Ethical Guidelines for Clinical Studies (2014, Ministry of Education, Culture, Sports, Science and Technology and Ministry of Health, Labour and Welfare Notification No.3, partial revision on 28 February, 2017), in principle.

Amendment

Purpose of amendment:

The purpose of this amendment is to make a clarification of typo this protocol.

Current study status:

Case Report Form Revision Required: Yes No

1. INTRODUCTION

(1) Circumstances

Presbyopia is defined as the normal loss of accommodation that occurs with age¹⁾, where the cause of the loss is associated with the sclerosis of crystalline lens¹⁾. It has been reported that the sclerosis of crystalline lens exponentially increases at around age 45¹⁾. While there are many ways to correct presbyopia such as eye glasses, contact lenses (CL) and keratomileusis (a corneal reshaping surgery to correct presbyopia or multifocal intra ocular lens)²⁾, the use of multifocal type CL (MFCL) to correct presbyopia is gradually increasing³⁾. However, it has been reported that there are more people who are discontinuing the use of CL due to discomfort and visual acuity issues above age 40 for whom it is considered necessary to correct presbyopia than the people below age 40⁴⁾.

Alcon Japan Ltd., has launched DAILIES TOTAL1[®] Multifocal (DT1MF), the silicone hydrogel contact lenses that are superior in comfort⁵⁾ in July, 2017. DT1MF adopts the optical design with progressive add power by adding add power to realize seamless visual performance concentrically⁶⁾. It is considered that center stability of MFCL on cornea when wearing CL is critical in terms of visual performance of contact lenses⁷⁾, lens centration, lens fitting, subjective ratings (overall quality of vision, lens comfort at the end of a day, visual performance (far, intermediate(distance) and near), eye fatigue (stiff shoulder, headache, dry eye, eye pain, heavy feeling in the back of eyes, eyestrain), lens comfort throughout the day), binocular VA (far, intermediate, near), corneal staining, conjunctival staining, lens surface wettability and lens deposit will be assessed in comparison to 1-Day ACUVUE[®] MOIST[®] Multifocal (AMMF)⁸⁾ contact lenses similar to DT1MF in the optical design which uses hydroxyethyl methacrylate in the material as a control.

This study will be conducted in accordance with Good Clinical Practice (GCP) and the Ethical Guidelines for Clinical Studies (2014, Ministry of Education, Culture, Sports, Science and Technology and Ministry of Health, Labour and Welfare Notification No.3, partial revision on 28 February, 2017), in principle.

(2) Summary of known and possible risks and benefits to subjects

Regarding the investigational devices assessed in this study, DT1MF and AMMF, Alcon Japan Ltd., and Johnson & Johnson K.K. Vision Care Company, respectively, were granted marketing approval in Japan in February 2017 and December 2014, respectively. The safety and efficacy information on the two investigational devices are described below.

1) Information on Safety

[1] Items common to DT1MF and AMMF

The following warnings and contraindications stated in direction for use are common to both investigational devices:

[Warnings]

- Contact lens wear could result in corneal epithelial problems including corneal ulcer, keratitis (including infectious keratitis), corneal infiltration, and corneal erosion, as well as corneal edema, conjunctivitis (including giant papillary conjunctivitis), iritis, and corneal neovascularization, and may accelerate a decrease in corneal endothelial cells.

[Contraindications]

- Acute and subacute inflammations of anterior eye segment
- Eye infection
- Uveitis
- Decreased corneal sensitivity
- Dry eye and lacrimal disease that may interfere with lens wear
- Eyelid abnormality
- Allergic disease that may affect lens wear
- Living environments constantly exposed to dryness
- Living environments liable to eye contamination with dust or drugs
- Other diseases inappropriate for lens wear

[2] Information on Safety for DT1MF

Information on device deficiency and adverse events stated in direction for use of DT1MF is described below:

Deficiency/Adverse events

The following deficiency and adverse events may occur:

(1) Device Deficiency

Lens: Tear, scratch, deformation, discoloration

(2) Adverse events

Corneal ulcer, corneal abscess, corneal perforation, corneal infiltration, corneal erosion, keratitis, Corneal epithelial disorders including corneal epithelial staining, corneal edema, corneal neovascularization, conjunctivitis(including allergic conjunctivitis and giant papillary conjunctivitis), subconjunctival hemorrhage, iritis, hordeolum, meibomitis, chalazion, accommodative asthenopia, dry eye, and decreased corneal endothelial cells, photosensitivity reaction(photophobia), rainbows and aureole around light

[3] Information on Safety for AMMF

Information on device deficiency and adverse events stated in direction for use of AMMF is described below:

Deficiency/Adverse events

The following deficiency and adverse events may occur:

(1) Device Deficiency

Lens: Tear, scratch, deformation, discoloration, foreign object, 2 lenses of more attached to each other in a layer

Preservative solution and package: Leakage, discoloration/deterioration of liquid, breakage, contamination

(2) Adverse events

Corneal ulcer, corneal abscess, corneal perforation, corneal infiltration, corneal erosion, keratitis, Corneal epithelial disorders including corneal epithelial staining, corneal edema, corneal neovascularization, conjunctivitis, subconjunctival hemorrhage, iritis, hordeolum, meibomitis, chalazion, accommodative asthenopia, dry eye, and decreased corneal endothelial cells

2. STUDY OBJECTIVES

The purpose of this clinical study is to demonstrate non-inferiority of DT1MF to AMMF for investigator-graded successful lens centration in Japanese population.

3. INVESTIGATIONAL PRODUCTS

(1) INVESTIGATIONAL PRODUCTS

Commercially available DTMF1 and AMMF products will be used in the study. A brief overview of the two investigational products is shown below.

Name of investigational products	DAILIES TOTAL 1® Multifocal	1-DAY ACUVUE® Moist® (Multifocal)
Approval number	22900BZX00026000	21600BZX00408000
Manufacturing and Distribution company	Alcon Japan Ltd.	Johnson & Johnson K.K. Vision Care Company
SCL IV Group	Group I	Group IV
Material (USAN)	Delefilcon A	etafilcon A
Water content [%]	33	58
Base curve [mm]	8.5	8.4
Diameter [mm]	14.1	14.3
Center thickness [mm] (for -3.00D)	0.09	0.084
Sphere power ranges [D]	-10.00 to -0.25, ±0.00 to +5.00	-9.00 to -0.25, ±0.00 to +5.00
Add power ranges [D]	+1.25D, +2.00D, +2.50D	+1.25D, +1.75D, +2.50D
Preservative solution	Phosphate buffered saline	Boric-acid buffered saline

(2) Usage

Follow each product's direction for use.

(3) Instructions on package and labeling

In accordance with the instructions for commercially available DTMF1 and AMMF products.

In order to keep the subject masked, the blister packages of the investigational products must be put in a seal to conceal the product name from the subjects before dispensing at each study site.

(4) Storage and Management

Commercially available products that are stored and managed by contact lens distributors will be used in this clinical study. The products will not be stored or managed at each study site. The site must get the products prescribed by the investigator, and dispense them with the seal that is described in (3) above. The dispensed study contact lenses will not have to be retrieved even in the case of used or unused. As an exception, DT1MF with any device deficiencies should be retrieved from the subject and returned to the Sponsor if at all possible.

- 10) Use of mechanical eyelid therapy or eyelid scrubs within 14 days before Visit 1 and not willing to discontinue during the study.
- 11) Eye injury or surgery within twelve weeks immediately prior to enrollment for this trial.
- 12) Enrollment of the investigator or his/her staff, family members of the investigator, family members of the investigator's staff, or individuals living in the households of these individuals.
- 13) Participation in any clinical trial within 30 days of the enrollment visit.
- 14) Patient who is judged ineligible as patients in this clinical study by the investigator.

[Rationale for exclusion criteria]

- 1) and 12): To prevent bias.
- 2), 3), 7), 9), 11) and 13): As per ISO 11980:2012; 4.2.1.1.b
- 4) Bilateral wear required.
- 5) Monovision may affect the quality of vision and could confound efficacy assessments.
- 6) Abnormal findings would contraindicate lens wear.
- 8) As per ISO 11980:2012; 4.2.1.1.
- 10) This may interfere with efficacy assessments.
- 14) This criterion was established for general safety considerations.

5. STUDY DESIGN

Prospective Multi-Center, Randomized^{*1}, Single Masked (Subject), Crossover study.

6. STUDY PROCEDURE

(1) Outline

Subjects will be randomly assigned to one of the two sequences of the investigational products (DT1MF and AMMF) and will wear each of the two investigational products in both eyes for at least 11 days each. Randomization manager will create the randomization code for the orders of the investigational product wearing (DT1MF→AMMF or AMMF→DT1MF) at a ratio of 1:1 using the permuted block method. The randomization manager will create the randomization code for the study eye (right or left) and maintain the key code in a masked state^{*2}, until the time of code breaking.

*1: The sequence of study lens use (DT1MF→AMMF, AMMF→DT1MF) is randomized in this study. The subjects wear the same lens in both eyes.

*2: The randomization code for sequence of study lens use will be masked only to the subjects. The randomization code for the study eye must be masked for the site, the subjects and sponsor.

(2) Examinations Schedule

Table Examinations Schedule

Procedure/ Assessment	Visit 1		Visit 2*1		Visit 3*1	Un-scheduled Visit
	Baseline	Disp. CL 1	Follow Up CL 1	Disp. CL 2	Follow up CL 2	
Informed consent						
Demographics [Gender, age, habitual multifocal SCL/SHCL (product name, diopter, the average number of hours of wear per day, the average number of days of wear per week)]			 *2		 *2	
Medical history/ Concurrent disease/ Concomitant medications						
Objective refraction						
Corneal curvature radius (K value)						
Subjective refraction						
VA	Best corrected visual acuity with trial frame 					[]
Biomicroscope: Slit-lamp examination	 *3		 *3		 *3	[ *3]
CL parameter selection						[]
Study lenses dispensing*4						[]
Lens centration assessment						[]
Verify inclusion/exclusion criteria						
Adverse events, Device Deficiencies	 *6					

[]: To conduct examinations/observations as needed

*1: Allowance for next visit: the day after 14 ± 3 days from the present visit.

*2: Confirm frequency of Lens 1 or Lens 2 wear (average number of hours per day, number of total days).

*3: Including observations of fluorescein corneal and conjunctival staining.

[figure not shown]
*4: Record information of dispensed CL (DT1MF or AMMF) diopter, and lot number.

*5: [REDACTED]

*6: Document the untoward event that occurred from getting informed consent to the use of the investigational products.

(3) Method of subject enrollment

A flow of subject enrollment is shown below.

1) Subject information and informed consent

After an explanation of the study details is given to a prospective subject, his/her consent to participate in the study will be obtained.

2) Assignment of subject identification code

The subject identification code will be assigned to a subject assessed to be eligible for the study.

3) Eligibility screening

The investigator will assess the eligibility of the subject through examinations and observations needed to assess the eligibility based on the inclusion and exclusion criteria (eligibility screening).

4) Notification to the enrollment registration center

Information of the subject whose eligibility is confirmed will be sent by fax or other means to the registration center. The center will send back the randomization form, which indicates the sequence of contact lens dispensing (DT1MF→AMMF or AMMF→DT1MF).

5) Examinations/observations

Examinations and observations will be performed as specified after Section 6 “Study Procedure”, (4) “Examinations Procedure 2) Visit1: “At dispensing Lens 1”.

(4) Examinations Procedure

To conduct the following examinations at Visit 1, Visit 2 and visit 3. The tests that are generally performed when

prescribing contact lenses can be used as data for clinical study even if such data are from the tests performed before obtaining informed consent. The sequence of the examination procedures can be changed at this clinical study sites. CL parameter selection will be followed each manufacturer's recommended fitting guide.

1) Visit 1: Baseline visit

- [1] After giving a full explanation of the study details to each subject, the investigator will obtain voluntary written informed consent from the subject. The subject identification code will be assigned to a subject assessed to be eligible for the study.
- [2] Collect the information on subject demographics (gender, age, habitual multifocal SCL/SHCL information [brand name, sphere and add powers, average number of hours of wear per day and the average number of days of wear per week]), ocular medical history (up to 12 weeks before informed consent), ocular surgery history, complication, and concomitant medications.
- [3] As subjective questionnaires, provide the subject with "Subject Questionnaire Forms" (for wearing habitual multifocal SCL/SHCL) and collect the forms within a day after the subject completes the questionnaires at the study site.
- [4] Measure binocular VA at 5m, 70cm and 30cm when wearing habitual multifocal SCL/SHCL.
- [5] Perform refractometry and keratometry to measure objective refraction and corneal curvature radius. Perform subjective refraction to measure best corrected visual acuity with an ophthalmoscope.
- [6] Assess fluorescein corneal and conjunctival staining by slit-lamp microscopy according to Section 6-(5) "Evaluation Method" (5) "Corneal staining" and Section6-(5) "Evaluation Method", 6) "Conjunctival staining"
- [7] Select the parameters for investigational product 1 (Lens 1) and investigational product 2 (Lens 2) (lens centration [REDACTED] assessment (according to Section 6-(5) "Evaluation method" (1) "Lens Centration" [REDACTED] [REDACTED])
- [8] Confirm the presence or absence of adverse events and device deficiencies. If any adverse event and/or device deficiencies is present, record data on the event in the Adverse Event CRF according to Section 10 "Adverse Events and Device Deficiencies, etc." of the protocol. The already existing symptoms and diseases at obtaining informed consent are regarded as complications. The events that are developed anew or aggravated after informed consent are recorded as adverse events.
- [9] If the subject is assessed to be eligible for the study based on these examination results and the inclusion and exclusion criteria, information on the subject will be sent to the registration center by fax or other means.
- [10] Receive the randomization form for the sequence of contact lens dispensing from the registration center by fax or other means.

2) Visit 1: Disp. CL 1

- [1] Observe the ocular anterior segment with Lens 1 by slit-lamp microscopy.
- [2] Assess lens centration [REDACTED] (10-15 min post insertion) for Lens 1 by slit-lamp microscopy

according to Section 6-(5) "Evaluation Method", 1) "Lens centration" [REDACTED]
[REDACTED]

- [3] If any specification adjustment is required, repeat the procedures from [1] to [3] above.
- [4] [REDACTED]
- [5] Confirm information on the dispensed Lens 1 (type, diopter and lot number).
- [6] Confirm the presence or absence of adverse events and device deficiencies. If any adverse event and/or device deficiencies is present, record data on the event in the Adverse Event CRF according to Section 10 "Adverse Events and Device Deficiencies, etc." of the protocol.
- [7] Schedule the next visit (Visit 2) date. Dispense necessary number of Lens 1 to the subject. Instruct the subject to contact the investigator, etc. if he/she feels any abnormality. If lens has any device deficiencies, let the subject bring it on Visit 2.

3) Visit 2: Follow up CL1

- [1] Confirm the time of Lens 1 insertion and the start and end times of examinations on the visit day (and document these times in the medical record).
- [2] Confirm the change of concomitant medications, etc.
- [3] Confirm whether Lens 1 is used appropriately during the period between the last and present visits (total days of Lens 1 wearing, average of wearing time per day. If subjects visit the clinic without wearing Lens 1, confirm the reason).

[REDACTED]
[REDACTED]
[REDACTED]

- [7] Assess lens centration [REDACTED] for Lens 1 by slit-lamp microscopy according to Section 6-(5) "Evaluation Method", 1) "Lens centration" [REDACTED]
[REDACTED]
- [8] Remove Lens 1, and assess fluorescein corneal and conjunctival staining by slit-lamp microscopy according to Section 6-(5) "Evaluation Method" 5) "Corneal staining" and Section 6-(5) "Evaluation Method", 6) "Conjunctival staining"
- [9] Measure best corrected visual acuity with trial frame.
- [10] Confirm the presence or absence of adverse events and device deficiencies with reference to subjective questionnaire answers. If any adverse event and/or device deficiencies is present, record data on the event in the Adverse Event CRF according to Section 10 "Adverse Events and Device Deficiencies, etc." of the protocol.

4) Visit 2 Disp. CL 2

- [1] Observe the ocular anterior segment with Lens 2 by slit-lamp microscopy.

- [2] Assess lens centration [REDACTED] (10-15 min post insertion) for Lens 2 by slit-lamp microscopy according to Section 6-(5) "Evaluation Method", 1) "Lens centration" [REDACTED]
[REDACTED]
- [3] If any replacement in specification is required, repeat the procedures from 1 to 3 above.
[REDACTED]
- [5] Confirm information on the dispensed Lens 2 (type, diopter and lot number).
- [6] Confirm the presence or absence of adverse events and device deficiencies. If any adverse event and/or device deficiencies is present, record data on the event in the Adverse Event CRF according to Section 10 "Adverse Events and Device Deficiencies, etc." of the protocol.
- [7] Check the date of the next visit (Visit 3), and tell the subject to bring habitual multifocal SCL/SHCL or glasses when follow up visit. Dispense necessary number of Lens 2 to the subject. Instruct the subject to contact the investigator, etc. if he/she feels any abnormality. If lens has any device deficiencies, let the subject bring it on Visit 2.

5) Visit3: Follow up CL2

- [1] Confirming the time of Lens 2 insertion and the start and end times of examinations on the visit day (and document these times in the medical record).
- [2] Confirm the change of concomitant medications, etc.
- [3] Confirm whether Lens 2 is used appropriately during the period between the last and present visits (total days of Lens 2 wearing, average of wearing time per day). If subjects visit the clinic without wearing Lens 2, confirm the reason.

[REDACTED]
[REDACTED]
[REDACTED]
[REDACTED]
[REDACTED]
[REDACTED]

- [7] Assess lens centration [REDACTED] for Lens 2 by slit-lamp microscopy according to Section 6-(5) "Evaluation Method", 1) "Lens centration" [REDACTED]
[REDACTED]
- [8] Remove Lens 2, and assess fluorescein corneal and conjunctival staining by slit-lamp microscopy according to Section 6-(5) "Evaluation Method", (5) "Corneal staining" and Section6-(5) "Evaluation Method", (6) "Conjunctival staining"
- [9] Measure best corrected visual acuity with trial frame.
- [10] Confirm the presence or absence of adverse events and device deficiencies with reference to subjective questionnaire answers. If any adverse event and/or device deficiencies is present, record data on the event in the Adverse Event CRF according to Section 10 "Adverse Events and Device Deficiencies, etc." of the protocol.

6) **Unscheduled Visit (To conduct examinations as needed)**

- [1] At unscheduled visit resulting from adverse events, etc., confirm the reason for visit and procedures taken during the visit.
- [2] Identify the type of the study lens used by the subject.
- [3] Perform examinations, assessments, or confirmations considered necessary by the investigator among those listed below:
 - Best corrected visual acuity with trial frame
 - [REDACTED]
 - Lens centration [REDACTED]
 - Slit-lamp microscopy examination (including sodium fluorescein corneal, etc.).
 - Information on the investigational products (diopter and lot number), if changed
 - [REDACTED]
- [4] Dispense the required number of the study lens to the subject, as needed.
- [5] Confirm the presence or absence of adverse events. If any adverse event is present, confirm the items in the Adverse Event CRF according to Section 10 “Adverse Events and Device Deficiencies, etc.” of the protocol.

(5) **Evaluation Method**

1) **Lens centration**

Assess lens centration for each eye by slit-lamp microscopy according to the criteria shown below.

For assessment results other than “Optimal”, check the direction of lens decentration (upward, downward, nasal, or temporal).

[figure not shown]
	Criteria
0	Centered/ Optimal
1	Slight decentration
2	Mild decentration (without limbal touch)
3	Moderate decentration (with limbal touch but without corneal exposure)
4	Severe decentration (with corneal exposure)

[figure not shown]
2) [REDACTED]

[figure not shown]
[REDACTED]

[REDACTED]

[REDACTED]

[figure not shown]
4) Fluorescein corneal and conjunctival staining

Corneal and conjunctival staining with fluorescein of both eyes will be rated by the investigator using a 5 point scale (0= Normal, 1= Trace, 2=Mild, 3=Moderate, 4=Severe).

Corneal staining with fluorescein (EFRON GRADING)

Conjunctival staining with fluorescein (EFRON GRADING)

(6) Anticipated study period

From NOVEMBER 2017 to OCTOBER 2018

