5.3.2 Best corrected visual acuity with trial frames

For best corrected decimal visual acuity with trial frame, descriptive statistics (mean, mean \pm dispersion factors (DF), N, median, min and max) will be provided.

In order to compute the mean of decimal visual acuity correctly, the geometric mean must be used for uncorrected distance visual acuity and best corrected distance visual acuity.

The formulas for transforming from decimal acuity to logMAR score and back are as follows.

$$\text{LogMAR} = -\text{Log}_{10} (\text{Decimal Acuity})$$

$$\text{Decimal Acuity} = \text{antiLog} (-\text{LogMAR}) = 10^{-\text{LogMAR}}$$

For reference, the mean of decimal acuity is defined as follows.

$$\text{Mean of Decimal Acuity} = 10^{\text{mean of} (-\text{Log MAR})} = 10^{\text{mean of Log10 (Decimal Acuity)}}$$

For geometric means, dispersion factors (DF) corresponds to standard deviations and defined as:

$$+DF = 10^{(\text{mean of Log10 (Decimal Acuity)} + \text{Log (SD)})} - 10^{\text{mean of Log10 (Decimal Acuity)}}$$

$$-DF = 10^{(\text{mean of Log10 (Decimal Acuity)})} - 10^{(\text{mean of Log10 (Decimal Acuity)} - \text{Log (SD)})}$$

where, Log (SD) is a standard deviation of Log₁₀ (Decimal Acuity).

The number and percentage of eyes with best corrected visual acuity decrease from the dispending visit to the follow-up visit will be presented by each investigational product.

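### By default, best corrected acuity is read before fluorescein at Visit 1 but after it at Visits 2 and 3, so the descriptive count of eyes with decreased acuity may be inflated for both products

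*Protocol*

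**What the plan says.** **Visit 1** (Protocol 6(4), baseline visit). Step [5] reads: "Perform subjective refraction to measure best corrected visual acuity with an ophthalmoscope". Fluorescein staining follows as step [6].

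**Visits 2 and 3** (Protocol 6(4), follow-up of CL1 and CL2). Step [8] at Visit 2 is "Remove Lens 1, and assess fluorescein corneal and conjunctival staining by slit-lamp microscopy", and at Visit 3 it is "Remove Lens 2, and assess fluorescein corneal and conjunctival staining by slit-lamp microscopy". In both, step [9] comes next: "Measure best corrected visual acuity with trial frame".

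**Freedom to reorder.** The opening of Protocol 6(4) states: "The sequence of the examination procedures can be changed at this clinical study sites". It makes no exception for acuity relative to fluorescein.

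**Analysis.** SAP 5.3.2 will present, by product, "The number and percentage of eyes with best corrected visual acuity decrease from the dispending visit to the follow-up visit". It sets no minimum size for a decrease. Protocol 9(6) instead summarises safety variables as changes from baseline. SAP Table 1-1 makes Visit 2 both the follow-up for the first lens and the dispensing visit for the second, and the protocol's examination schedule shows a single acuity reading there. SAP 5.2 says that there are no formal safety hypotheses. Acuity is one of the four safety endpoints in SAP 5.1.

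**The concern.** A change score is easiest to interpret when both readings are taken under the same conditions. Here the written default places dye and a staining examination between lens removal and the acuity reading at follow-up, but not before the reading at Visit 1. No reason is given. If that exposure lowers acuity even slightly, some eyes will be counted as having lost acuity because of the examination order and not because of the lens.

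Safety is reported descriptively, so the percentages are themselves the result and no test or model would absorb such an artefact. Because the SAP counts a decrease of any size, a small systematic shift is enough to move eyes into the count, and a real decrease becomes harder to see.

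**Working it through.** **1. Trace the order.** This is the listed default, which sites may change.

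| Visit | Acuity | Fluorescein staining | Acuity reading is |
|---|---|---|---|
| 1 | step [5] | step [6] | pre-dye |
| 2 | step [9] | step [8] | post-dye |
| 3 | step [9] | step [8] | post-dye |

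**2. Map the readings to the contrasts.**

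| Contrast | SAP 5.3.2 (from dispensing visit) | Protocol 9(6) (from baseline) |
|---|---|---|
| Lens 1 | Visit 1 to 2: pre to post | Visit 1 to 2: pre to post |
| Lens 2 | Visit 2 to 3: post to post | Visit 1 to 3: pre to post |

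Under the SAP's reference only Lens 1 is mismatched. Under the protocol's reference both lenses are.

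**3. Size under assumptions.** The documents give no figure for acuity decrease, so there is nothing to reproduce, and every input here is assumed. For 400,000 eyes, true logMAR is drawn from N(-0.08, 0.08) with no true change. Each reading adds error with SD 0.03, 0.05 or 0.07 and is rounded to the nearest step of a decimal chart (0.3 to 1.0 by tenths, then 1.2 and 1.5). Post-dye readings are worse by a shift of 0, 0.02 or 0.05 logMAR. The percentage of eyes with any decrease in the Lens 1 contrast is:

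| Shift (logMAR) | SD 0.03 | SD 0.05 | SD 0.07 |
|---|---|---|---|
| 0 | 18.7 | 26.4 | 30.6 |
| 0.02 | 32.0 | 36.3 | 38.5 |
| 0.05 | 56.4 | 52.8 | 51.0 |

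Rise over no shift:
- 0.02: 32.0 - 18.7 = 13.3; 36.3 - 26.4 = 9.9; 38.5 - 30.6 = 7.9 points.
- 0.05: 56.4 - 18.7 = 37.7; 52.8 - 26.4 = 26.4; 51.0 - 30.6 = 20.4 points.

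The range is therefore about 8 to 38 points. In the same simulation the Lens 2 contrast, where the shift applies to both readings, rises by about 2 points at 0.02 and about 4 at 0.05. The cause is uneven chart steps: the step from 1.5 to 1.2 is log10(1.5/1.2) = 0.097 logMAR, but from 1.0 to 0.9 it is log10(1.0/0.9) = 0.046. Eyes shifted into the finer part of the chart cross a step more often through reading error alone.

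**4. Effect on each product's rate.** With 1:1 sequences, each product is Lens 1 in about half of subjects, so its rate rises by the mean of the two contrasts:
- 0.02: (7.9 + 2)/2 = 5.0 to (13.3 + 2)/2 = 7.7 points.
- 0.05: (20.4 + 4)/2 = 12.2 to (37.7 + 4)/2 = 20.9 points.

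**5. Effect on the product comparison.** Let a and b be the numbers in the two sequences, and q1 and q0 the Lens 1 and Lens 2 rates. The product difference is (a - b)(q1 - q0)/(a + b).
- With 67/67 it is 0.
- With 63/71 and illustrative rates of 30% and 10%, the products show (63 × 0.30 + 71 × 0.10)/134 = 19.4% and (71 × 0.30 + 63 × 0.10)/134 = 20.6%, a gap of 1.2 points. With 5% and 2% the gap is 0.2.
- The most extreme case in step 3 has a Lens 1 minus Lens 2 excess of 37.7 - 4 = 33.7 points. With 63/71 it gives 8/134 × 33.7 = 2.0 points.

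**The case against.** **The listed order is only a default.** This stands. Sites may change it, and routine tests done before consent may serve as study data, so one cannot say that acuity will be measured in these orders. The permission does not cure the mismatch, though: it sets no limit on where acuity falls relative to dye, so conditions may also vary by site and visit. The schedule table puts acuity above the slit-lamp row, but its rows are not in time order, since eligibility is verified below lens dispensing.

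**The mechanism comes from outside the documents.** This stands. Nothing in either document says that fluorescein or slit-lamp light lowers best corrected acuity. The simulated rise depends directly on the assumed shift. Even with no shift, 19% to 31% of simulated eyes show a decrease. That reflects the missing size threshold, which reordering steps would not remove.

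**Stronger readings that the documents do not support.** A reader might infer any of the following:
- *Both lenses are compared on unlike readings.* Under the SAP's reference, the listed Lens 2 contrast is like with like.
- *All the excess falls in the first period.* Step 3 shows a smaller rise for Lens 2 as well.
- *Lens removal differs between visits.* At Visit 1 step [4] is "Measure binocular VA at 5m, 70cm and 30cm when wearing habitual multifocal SCL/SHCL", so those lenses presumably also come off before refraction in step [5].
- *One product is favoured.* Randomised sequence spreads the artefact over both products, and the SAP presents the count by product.
- *The primary result is at risk.* Centration is graded at step [7], before lens removal and dye.

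**Conclusion.** The point holds in a limited form. The default order of acuity and fluorescein differs between Visit 1 and Visits 2 and 3, and nothing standardises it. This leaves the Lens 1 contrast mismatched under the SAP's reference, and both contrasts mismatched under the protocol's.

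The consequence is conditional on a post-dye loss of acuity, which is assumed here and not shown. Under shifts of 0.02 to 0.05 logMAR, each product's percentage with a decrease would be overstated by about 5 to 21 points under the SAP's reference. If the true shift is zero, there is no order artefact. Severity is low: this is one descriptive safety count, and the product comparison and the primary endpoint are not materially affected. It merits action because the correction is free and makes the dye condition the same under either reference visit.

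**What to change.** 1. At Visits 2 and 3, exchange steps [8] and [9] in part: remove the lens, measure best corrected acuity, then instil fluorescein and grade staining, as at Visit 1.
2. Exempt this order from the general permission to change the examination sequence.
3. In the same edit, reconcile two conflicts on this endpoint. Visit 1 step [5] names an ophthalmoscope, while the examination schedule names a trial frame. Protocol 9(6) takes change from baseline, while SAP 5.3.2 takes decrease from the dispensing visit.

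The cost is wording in the protocol and SAP, with no added procedure, visit or staff. The swap removes the difference in dye and staining examination. It does not remove the slit-lamp grading of centration at step [7], which is done with the lens on and would still precede acuity at the follow-up visits.
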